### 6.3.7 Endpoints Related to RBC Transfusion

These endpoints address RBC transfusion for the entire length of study, by the four analysis time periods in Year 1 (see [Section 5.1](#)), and in the long-term treatment/follow-up period (Week 52 to EOS) unless otherwise specified.

- Receipt of any RBC transfusion
- Time to first RBC transfusion (for entire study)
- Total number of RBC transfusion episodes received
- Rate of RBC transfusions, calculated as the number of episodes divided by the duration of at-risk follow-up in person-years

RBC transfusion may be considered rescue when “Worsening Anaemia due to CKD” is the reason indicated on the CRF.

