5.3 Secondary Efficacy Endpoints

The key secondary efficacy endpoints include the following:

- Mean change in Hb value between Baseline (mean pretreatment Hb) and the secondary evaluation period (Weeks 40-52)
- Proportion of subjects with Hb values within the target range during the primary evaluation period (Weeks 24-36)
- Proportion of subjects with Hb values within the target range during the secondary evaluation period (Weeks 40-52)

Other secondary efficacy endpoints include:

- Proportion of time with Hb values within the target range during the primary evaluation period (Weeks 24-36)
- Proportion of time with Hb values within the target range during the secondary evaluation period (Weeks 40-52)
- Proportion of subjects with Hb increase of >1.0 g/dL from Baseline

- Time to achieve Hb increase of >1.0 g/dL from Baseline
- Mean change in Hb between Baseline (mean pretreatment Hb) and the primary evaluation period (mean Hb from Weeks 24-36) stratified by pre-baseline ESA exposure
- Progression of CKD
- Proportion of subjects receiving IV iron therapy from Baseline visit to Week 52
- Mean monthly dose of IV elemental iron administered from Baseline to Week 52 in subjects who have received IV iron
- Proportion of subjects receiving RBC transfusion(s) from Baseline to Week 52
- ESA rescue
- Dose adjustments from Baseline to Week 52
-

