### **6.3.3 Endpoints Related to Iron**

These sections address iron-related endpoints from randomization through the end of the trials. The study population will be divided into the following baseline iron groups:

- 0 – those not receiving any iron at baseline,
- I – those receiving only oral iron at baseline,
- II – those receiving only intravenous (IV) iron at baseline, and
- III – those receiving IV and oral iron at baseline.

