## Statistical Analysis Plan AKB-6548-CI-0014 and AKB-6548-CI-0015

| Endpoint   | Approach to Analysis  | Comments   |
|--|---|--|
| Hepcidin, Ferritin, TIBC   | Four outcomes – change from baseline to PEP, change from baseline to SEP, percentage change from baseline to PEP, and percentage change from baseline to SEP.

Analysis of covariance stratified by baseline strata for change from baseline to PEP or SEP. | This analysis will use only observed data  |
| Serum Iron   |   |  |
| TSAT   |   |  |
| Other laboratory endpoints ( Section 6.3.4 )                                 |   |  |
| Change from baseline in serum glucose and lipid parameters at PEP and SEP                    | ANCOVA stratified by baseline strata.   | No imputation.   |
| RBC transfusion endpoints ( Section 6.3.7 )                                  |   |  |
| Receipt of any RBC transfusion   | Mantel-Haenszel test stratified by the baseline strata  |  |
| Total number of RBC transfusions received (entire length of study)                           | See Appendix D .  | If the distribution is highly skewed either because of a large spike at zero or a long tail to the right (or both), other methods may be considered. |
| Dose adjustment ( Section 6.3.5 )  |   |  |
| Dose adjustments (entire length of study)  | Descriptive statistics  | Other methods may be considered.   |
| ESA and Rescue endpoints ( Section 6.3.8 and Section 6.3.9 ) |   |  |
| Receipt of any ESA rescue medication   | Mantel-Haenszel test stratified by the baseline strata  |  |
| Receipt of any rescue therapy (series of definitions from narrow to broad)                   | Mantel-Haenszel test stratified by the baseline strata  |  |

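### The SAP defines no Baseline-to-Week-52 proportion for RBC transfusion or IV iron, although protocol 5.3 does; the whole-study proportions it plans are not risks at any stated time

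*SAP*

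**What the plan says.** **Protocol (Amendment 7-COL), 5.3.** Among the other secondary endpoints are "Proportion of subjects receiving RBC transfusion(s) from Baseline to Week 52", "Proportion of subjects receiving IV iron therapy from Baseline visit to Week 52" and "Mean monthly dose of IV elemental iron administered from Baseline to Week 52 in subjects who have received IV iron". All three stop at Week 52.

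**SAP, transfusion.** Section 6.3.7 opens: "These endpoints address RBC transfusion for the entire length of study, by the four analysis time periods in Year 1", and the sentence ends "and in the long-term treatment/follow-up period (Week 52 to EOS) unless otherwise specified". The measures listed are receipt of any transfusion, time to first transfusion (entire study), number of episodes, and "Rate of RBC transfusions, calculated as the number of episodes divided by the duration of at-risk follow-up in person-years". Table 3 lists "Receipt of any RBC transfusion" for a stratified Mantel-Haenszel test and states no period. Appendix D.1 repeats the endpoint, also without a period. Appendix D.3 lists time to first transfusion. Its template code (Exhibit D 3) requests Kaplan-Meier estimates by arm at 0, 24, 36, 40 and 52.

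**SAP, iron.** Section 6.3.3 says: "These sections address iron-related endpoints from randomization through the end of the trials". Table 3 and D.1 treat receipt of at least one administration as a binary endpoint with no period. Only the average weekly dose is split by Year 1 period and Weeks 52 to end of study (C.1.4), and its denominator counts only weeks under follow-up (6.3.3.2).

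**Precedence and duration.** SAP Section 1 gives the SAP priority over the protocols. SAP 2.2 ties trial length to 631 adjudicated MACE across the two studies. Protocol 7.5.1 guarantees only the opportunity to reach Visit 13 (Week 36). The MACE SAP, 2.5.1, expects up to 36 months of follow-up with a mean of about 2 years.

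**The concern.** Two named protocol secondary endpoints will not be produced as the protocol defines them, and the SAP neither says that the horizon changed nor explains why.

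The whole-study proportion is a poor substitute. Each subject's chance of being counted depends on how long that subject was observed. That depends on entry date, on when the 631st MACE falls, and on death and withdrawal. A statement that x% were ever transfused then describes no fixed period. It cannot be set beside the protocol's endpoint or beside another trial's 52-week figure. Later follow-up also includes time after permanent discontinuation, when protocol 7.5.5.2 returns subjects to standard care, including ESAs and iron.

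**Working it through.** **1. Can any planned output be read as the Week 52 proportion?**

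| Output | Transfusion | IV iron |
|---|---|---|
| Whole-study proportion | Yes (6.3.7) | Yes (6.3.3) |
| Proportion in each of four Year 1 windows | Yes (6.3.7) | None stated |
| Proportion, Week 52 to end of study | Yes (6.3.7) | None stated |
| Rate per person-year | Yes (6.3.7) | No |
| Time to first event | Yes (D.3) | Not in the D.3 list |
| Single Baseline-to-Week-52 proportion | No | No |

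The four window proportions cannot be added, because a subject transfused in two windows counts twice. By SAP Table 1 they cover Days 2 to 406, and 406/7 = 58 weeks; Week 52 is Day 52 x 7 = 364. The closest transfusion output is the Kaplan-Meier estimate at 52. The template runs separately by arm, so it gives no between-arm difference at Week 52. It does not state the time unit, and it does not treat death as a competing event.

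**2. How long is follow-up?** The event target reproduces: 4 x (1.960 + 0.842)^2 / (ln 1.25)^2 = 631 after rounding up. At the assumed 10% a year in 3700 subjects, 631/0.10 = 6310 at-risk years, or 6310/3700 = 1.71 per subject. If all were followed equally this corresponds to 1.77 to 1.87 years, depending on whether 10% is read as an annual probability or as a hazard. That agrees with the stated means of 1.8 years (original protocol synopsis) and about 2 years (MACE SAP).

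**3. How far can the two proportions differ?** The documents give no transfusion or iron rate, so the Week 52 proportion p and the hazard shape k are assumptions. With equal follow-up of F years, the whole-study proportion is 1 - (1 - p)^(F^k), where k = 1 is a constant hazard.

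| p at Week 52 (assumed) | F = 1.8, k = 1 | F = 2.0, k = 1 |
|---|---|---|
| 5% | 8.8% (1.76x) | 9.8% (1.95x) |
| 10% | 17.3% (1.73x) | 19.0% (1.90x) |
| 20% | 33.1% (1.65x) | 36.0% (1.80x) |

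Worked case: 1 - 0.90^1.8 = 17.3%.

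At p = 10% and F of 1.8 to 2.0, a declining hazard gives 1.47x to 1.57x (k = 0.7) or 1.32x to 1.38x (k = 0.5), and a rising one (k = 1.3) about 2.0x to 2.3x. Spreading F uniformly from 36 weeks to 36 months (mean 1.84 years) gives 1.78x at a 10% Week 52 risk under a constant hazard. Over all the combinations tried, with p from 2% to 60%, the ratio ran from about 1.2 to 2.7.

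**4. Is the treatment effect diluted?** A simulation was run with assumed inputs: control transfusion hazard 8 to 12% a year, on-drug hazard ratio 1.3, discontinuation 15% v 25% a year with the control hazard afterwards, death 7% and loss 4% a year. The control proportion was 7.1 to 10.7% at Week 52 and 10.7 to 20.3% over the whole study. The risk ratio fell from about 1.25 to 1.20-1.23. The SAP's main scale for binary endpoints is the risk difference (Section 9), approximately control proportion x (risk ratio - 1):

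- Low end: 7.1 x 0.25 = 1.8 points at Week 52; 10.7 x 0.20 to 0.23 = 2.1 to 2.5 over the whole study.
- High end: 10.7 x 0.25 = 2.7 points at Week 52; 20.3 x 0.20 to 0.23 = 4.1 to 4.7 over the whole study.

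The difference grows.

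**The case against.** For transfusion, the SAP already plans much of what is needed: time to first event, an episode rate per person-year, Year 1 windows, a separate post-Week-52 period, and template code that prints an estimate at 52. On-treatment rescue is isolated in 6.3.9, where both definitions exclude therapy starting after permanent discontinuation. The windows are wider than the protocol's by design, to reduce missing values (SAP 5.1), so Day 406 is not a mistake. With only Week 36 guaranteed, a crude Week 52 proportion would also lack a common horizon.

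All of that stands, and it narrows the point. It does not supply a defined Week 52 proportion or a between-arm Week 52 difference for transfusion, and it does nothing for IV iron.

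A reader might infer more than the documents support:

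- **A fixed inflation of 1.5 to 2 times.** That range needs a roughly constant hazard, mean follow-up of 1.8 to 2 years and a Week 52 proportion of at most about 40 to 50%. Iron use that is front-loaded or already established would give less.
- **A diluted effect.** The risk ratio moves slightly towards 1 in the simulation, but the risk difference increases.
- **Bias between arms.** Administrative follow-up depends on entry date, which 1:1 randomization balances.
- **An affected iron dose.** It is averaged over weeks followed, so the ratio for proportions does not carry over.

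**Conclusion.** The point holds as a mismatch of definition. Protocol 5.3 fixes both proportions at Week 52; the prevailing SAP defines neither at that horizon. It is clearest for IV iron, which has no Week 52 proportion anywhere in the SAP. For transfusion, the nearest equivalent is a by-arm Kaplan-Meier value from generic code.

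The crude whole-study proportion is not a risk at any stated time, because follow-up runs from about 36 weeks to 36 months before death or withdrawal is counted. It will be larger than the Week 52 proportion, by an amount that rests on event rates and hazard shapes absent from the documents.

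Severity is minor. SAP 9.3 describes these endpoints as exploratory and without multiplicity correction, and no primary or key secondary conclusion depends on them.

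**What to change.** In SAP 6.3.3, 6.3.7, Table 3 and D.1, before database lock:

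- Define the analysed endpoints as any RBC transfusion, and any IV iron, from Day 1 to Day 364, matching protocol 5.3.
- Estimate the Week 52 cumulative incidence in each arm with death as a competing event and subjects censored at end of observation, and report a stratified between-arm difference with its 95% confidence interval. The MACE SAP (Section 4) already uses competing-risk methods for outcomes that exclude all-cause death.
- Label whole-study proportions as descriptive, beside the planned time-to-first-transfusion and person-year analyses, and state the period in every Table 3 row.

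The cost is SAP wording, a date cut-off in the derivation and one additional estimator; no new data are needed. The drawback is that fewer events enter the Week 52 comparison than the whole-study one, so its interval will be less informative about later use.

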### 6.3.8 Endpoints Related to ESA Usage

The study will consider the following efficacy endpoints specific to ESA usage for the entire length of study, by the four analysis time periods in Year 1 (see [Section 5.1](#)), and in the long-term treatment/follow-up period (Week 52 to EOS) unless otherwise specified.

- Receipt of any ESA medication (in the darbepoetin alfa arm, use only includes ESA other than darbepoetin alfa as well as increases in darbepoetin alfa the investigator specifically designates as rescue)
- Time to first ESA medication (for entire study)
- Total number and maximum duration of ESA episodes.

ESA medication may be considered rescue when any of the following reasons are indicated on the relevant version of the CRF:

- [Original CRF] “the subject experienced a clinically significant worsening of their anaemia or symptoms of anaemia (e.g., fatigue, weakness, shortness of breath, chest pain, confusion, or dizziness) compared with Baseline”
- [Original CRF] “the subject's HGB is <9.0 g/dL”
- [CRF updated mid-2018] “Worsening of symptoms of anemia and Hb <9.0 g/dL”
- [CRF updated mid-2018] “Investigator discretion not meeting protocol-defined rescue criteria”
- [CRF updated mid-2018] “Other Specify” which include either one of the 2 reasons from the original CRF

Analyzing the impact of pre-baseline or post-baseline ESA on vadadustat efficacy requires conversion of ESA dose into common units. The epoetin alfa analogues, darbepoetin alfa and methoxy polyethylene glycol epoetin beta (Mircera), will be converted to IV epoetin equivalent units per kilogram per week (U/kg/week).

The following conversions have been derived from published literature and input from clinical experts [[Paganini, 1995](#); [Kaufman, 1998](#); [Cremieux, 2006](#); [Gosselin, 2006](#); [Levin, 2008](#); [FDA 2011](#); [Jordan, 2012](#); [Choi, 2013](#); [Vega, 2014](#); [Wright, 2015](#)].

- Subcutaneous (SC) epoetin to IV epoetin: 1:1.25

|   | SC Epoetin | IV Epoetin |
|---|------------|------------|
| Darbepoetin alfa to epoetin                         | 1:160      | 1:200      |
| Methoxy polyethylene glycol-epoetin beta to epoetin | 1:176      | 1:220      |

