7.5.5.2 Permanent Discontinuation of Study Medication

Subjects who permanently discontinue study medication prior to global study completion are expected to continue to be followed post discontinuation of study medication. These subjects are to have their EOT visit at the time of permanent discontinuation of study medication have the Follow-up visit 4 weeks after the EOT visit and continue to be followed through global study completion. At global study completion, each subject will have an End of Study (EOS) assessment to complete participation in the study. Receipt of rescue therapy is not a reason for permanent study medication discontinuation. While receiving ESA rescue, subjects must temporarily discontinue study medication but should resume study medication following the end of rescue therapy.

For subjects who permanently discontinue study medication, the Investigator will resume standard of care treatment, including ESAs and iron therapy, as deemed appropriate.

It is important to continue to follow subjects that permanently discontinue study medication.

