### 6.3.9 Rescue Therapy: Series of Definitions

Rescue will be defined from narrow to broad, based on the type, timing, intensity, and reason for treatment. These treatments may be considered rescue therapy for anemia secondary to chronic kidney disease: ESA medication, and RBC transfusion.

The possible reasons for such treatments include:

- Investigator-ordered rescue (per protocol for worsening of anemia),
- Adverse events (unrelated to anemia),
- Maintenance during prolonged interruption of study treatment, and
- Inadvertent use (at hospital or dialysis center).

If a given therapy starts the same day as permanent discontinuation of study drug, then that therapy will be considered on treatment for rescue definitions.

For the vadadustat arm, any use of ESA may be considered rescue. For the control arm, the study drug itself is an ESA and so is not necessarily rescue, yet change to another ESA may be considered rescue. Because darbepoetin alfa is titratable, increase in dose is not considered rescue unless the investigator specifically designates it as such; however, increases in dose relative to last dose will be characterized in three categories by percentage increase: <50%,

Statistical Analysis Plan AKB-6548-CI-0014 and AKB-6548-CI-0015

$\geq 50\%$  and  $< 100\%$ , and  $\geq 100\%$ . Subjects will be presented by their maximum category of increase within each of the four analysis time periods in Year 1 (see [Section 5.1](#)). All ESA use will be converted to IV epoetin alfa equivalents.

The CRFs collect reasons for ESA medication and RBC transfusion. The series of rescue definitions are defined as follows:

- Narrow: Rescue for worsening anemia with ESA medication or RBC transfusion defined in [Section 6.3.7](#) and [Section 6.3.8](#), not starting after permanent study treatment discontinuation.
- Broad-on-treatment: Any exposure to ESA medication (aside from darbepoetin alfa not designated as rescue in the control arm) or RBC transfusion for any reason not starting after permanent study treatment discontinuation.

In addition to the sensitivity analyses ([Section 9.1.4](#)), the report will include a summary of the incidence, timing, duration, intensity, and frequency for each definition of rescue, including a Kaplan-Meier plot of time to first rescue.

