## D.3. Analysis of Time to Event Data

This section describes the methods for analyzing time-to-event endpoints, for example, time to:

- achieve 1g/dL increase in Hb in Year 1 (CI-0014)
- first rescue therapy (by series of definitions)
- first RBC transfusion
- first ESA use (aside from control arm medication not specified as rescue)
- progression of chronic kidney disease (CKD).
- study discontinuation

Time-to-event distributions will be estimated using the Kaplan-Meier product-limit method and log rank test.

The hazard ratio and corresponding 95% confidence interval for the comparison of vadadustat to darbepoetin alfa will be estimated using a Cox proportional hazards model, with treatment group and other predictors as covariates. Analyses in the randomized population will be stratified by the stratification factors; analyses in subgroups will be conducted similarly. The predictor variables (&PREDVAR. in [Exhibit D 3](#)) for hemoglobin-related events are baseline ESA dose (three

Statistical Analysis Plan AKB-6548-CI-0014 and AKB-6548-CI-0015

levels specified in [Section 11](#)) and continuous baseline Hb. For CKD progression, the predictor variable is continuous baseline eGFR.

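### The ESA-use endpoints in SAP 6.3.8 run to end of study but drop non-rescue darbepoetin in the control arm only, so the same non-study darbepoetin given off study drug counts in one arm and not the other

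*SAP*

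**What the plan says.** SAP 6.3.8 sets out "efficacy endpoints specific to ESA usage for the entire length of study", for the four Year 1 analysis periods, and "in the long-term treatment/follow-up period (Week 52 to EOS) unless otherwise specified". The endpoints are receipt of any ESA, time to first ESA, and the number and maximum duration of ESA episodes. For the control arm the rule is "Receipt of any ESA medication (in the darbepoetin alfa arm, use only includes ESA other than darbepoetin alfa", with one exception: "increases in darbepoetin alfa the investigator specifically designates as rescue". The section gives no cut-off or censoring at permanent discontinuation.

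SAP D.2 models the number of ESA episodes with a follow-up-time offset and no on-treatment limit. SAP D.3 lists time to "first ESA use (aside from control arm medication not specified as rescue", closing the parenthesis there.

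Protocol 7.5.5.2 (Amendment 7-COL) describes care after stopping: "For subjects who permanently discontinue study medication, the Investigator will resume standard of care treatment, including ESAs and iron therapy, as deemed appropriate". Protocol 8.5.2 likewise lifts the ban on non-protocol ESAs for rescue, for interruption for other reasons, and for permanent discontinuation.

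SAP 6.3.9, the next section, limits both its narrow and its broad-on-treatment rescue definitions to therapy "not starting after permanent study treatment discontinuation".

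**The concern.** Leaving darbepoetin out of the control-arm count makes sense while it is the assigned study drug: otherwise every control subject would be an event on Day 1. Once a control subject is off study drug, darbepoetin is ordinary care in both arms and that reason is gone. The 6.3.8 exclusion nevertheless continues to end of study.

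All CI-0015 subjects are on an ESA at entry (Protocol 7.2, criterion 3), so going back to one after stopping is the expected course. Two arms with identical behaviour would then show different ESA use, and the gap would grow with discontinuation and with length of follow-up. A Cox hazard ratio or an episode-count model built on this rule would be read as comparative need for ESA, when part of it is the counting rule.

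**Working it through.** The documents give no rate, power or sample size for the ESA-use endpoints, so there is no planned figure to reproduce. The check has two parts.

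**1. What counts, by arm, under 6.3.8 as written**

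| Situation | Vadadustat arm | Control arm |
|---|---|---|
| On study drug, non-darbepoetin ESA | event | event |
| On study drug, control-arm darbepoetin increase designated rescue | not applicable | event |
| Off study drug, epoetin or methoxy polyethylene glycol-epoetin beta | event | event |
| Off study drug, non-study darbepoetin as standard care | event | **not an event** |

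The last row is the defect. It applies after permanent discontinuation and also during an interruption in which Protocol 8.5.2 allows a non-protocol ESA.

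**2. How large the artefact could be (assumed inputs, same behaviour in both arms)**

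*Proportion with any ESA.* Let p0 be the on-treatment event probability, d the probability of stopping, q the probability of resuming an ESA, and s the share of resumed ESA that is darbepoetin.

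- Vadadustat: p0 + (1 − p0)dq
- Control: p0 + (1 − p0)dq(1 − s)
- Spurious difference: (1 − p0)dqs

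Mid case p0 = 0.10, d = 0.25, q = 0.50, s = 0.50:

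- Vadadustat: 0.10 + 0.90 × 0.125 = 0.2125
- Control: 0.10 + 0.90 × 0.0625 = 0.15625
- Difference: 5.6 percentage points. At 925 per arm (SAP 2.6) the chance of a nominal two-sided p < 0.05 is about 88%.

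Over p0 10–20%, d 10–40%, q 50–80% and s 25–75%:

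- Smallest difference: 0.80 × 0.10 × 0.50 × 0.25 = 1.0 point, with about a 7% chance of nominal significance.
- Largest difference: 0.90 × 0.40 × 0.80 × 0.75 = 21.6 points, with a chance near 100%.

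*Event rates over time.* Assume an on-treatment rescue hazard r = 0.10 per year, a discontinuation hazard d per year, 80% of stoppers resuming an ESA at once, a darbepoetin share s, and follow-up uniform from 0.7 to 3 years. Let A be the mean of 1 − exp(−(r + d)T) over follow-up T. The probability of an event is A(r + 0.8d)/(r + d) for vadadustat and A(r + 0.8d(1 − s))/(r + d) for control.

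Example, d = 0.15 and s = 0.5, where A = 0.362:

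- Vadadustat: 0.362 × 0.22/0.25 = 31.8%
- Control: 0.362 × 0.16/0.25 = 23.1%

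Simulation of 400,000 subjects per arm gave:

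| d | s | Vadadustat | Control | Ratio of event rates |
|---|---|---|---|---|
| 0.15 | 0.5 | 31.7% | 23.2% | 1.46 |
| 0.15 | 0.8 | 31.7% | 18.0% | 1.95 |
| 0.30 | 0.5 | 42.9% | 27.8% | 1.74 |
| 0.30 | 0.8 | 42.9% | 18.7% | 2.77 |

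A repeat run gave 1.47, 1.95, 1.74 and 2.79. With only on-treatment ESA counted, the ratio was 0.99 to 1.01 in every scenario. That run has no interruptions, so it does not show that a cut-off at permanent discontinuation removes the interruption part of the asymmetry.

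**The case against.** The case for leaving the plan alone has several strong parts.

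- **Exposure is narrower than it looks.** A reader might infer that every post-discontinuation ESA is counted in one arm only. That holds only for darbepoetin. A reader might also infer that the listed Mantel-Haenszel comparison is biased. Table 3 and D.1 name receipt of ESA rescue medication, which depends on the reasons recorded on the CRF, so routine ESA after stopping does not automatically enter it. Both limits stand.
- **D.3 is ambiguous.** Its control arm medication could mean assigned study medication, in which case commercial darbepoetin after stopping would count. That is a possible reading, but 6.3.8 has no such wording, so the text still needs settling.
- **An on-treatment comparison already exists.** 6.3.9 provides incidence, timing, duration, frequency and a Kaplan-Meier plot. It combines ESA with transfusion, so it only partly substitutes.
- **A cut-off alone is an imperfect remedy.** It leaves the asymmetry during interruptions. Lack of efficacy is also a recognised reason for stopping (Protocol 7.5.5), so a vadadustat subject who stops for failure and starts an ESA the next day would drop out of the count. Both points stand and shape the fix.
- **Post-EOT data may be thin.** Protocol 9.2.1 records medications to the final protocol-required visit, Appendix A footnote [x] only through EOT, and SAP 2.2 continues rescue assessments to EOS. Poor capture would shrink the artefact without making the rule symmetric.
- **The stakes are limited.** SAP 9.3 treats these endpoints as exploratory and uncorrected for multiplicity, and the bias cannot produce a false result in favour of vadadustat.

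**Conclusion.** The concern holds in a limited form. Receipt of any ESA, time to first ESA (D.3 read literally) and ESA episode number and duration use an arm-specific counting rule that continues after its justification has ended. Non-study darbepoetin taken off study drug is an event in the vadadustat arm only.

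The size is unknown. The ratios of about 1.5 to 2.8 are ratios of event rates under assumed inputs and full capture of ESA use after EOT. A reader might take them as predicted hazard ratios for this trial, but the documents give no discontinuation, resumption or darbepoetin-share figure to support that. The lower end of the proportion calculation is about 1 percentage point.

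Nor should a reader infer a threat to the main conclusions. The primary and key secondary Hb analyses do not use this rule, and the sensitivity analyses that rest on 6.3.9 do not take in therapy started after permanent discontinuation. The change should be made because a formal model would otherwise report a treatment contrast that is partly a derivation artefact, and the SAP already contains most of the remedy.

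**What to change.** In SAP 6.3.8, D.2 and D.3:

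1. Limit the control-arm exclusion to darbepoetin given as assigned study medication. Non-study darbepoetin then counts in both arms, including during interruptions.
2. Make the main ESA-use comparison on-treatment: count ESA that starts on or before permanent discontinuation, with the same-day rule of 6.3.9. Match the D.2 follow-up offset and the D.3 censoring date to that window.
3. Report ESA use while off study drug, after permanent discontinuation and during interruptions, as a separate display. Count any ESA, including non-study darbepoetin, identically in both arms. Keep the whole-study and Week 52 to EOS summaries only on this footing.
4. Confirm how far ESA use is recorded after EOT, and reconcile Protocol 9.2.1, Protocol Appendix A footnote [x] and SAP 2.2.

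The cost is SAP wording and a derivation rule; no clinical procedure changes. The main endpoint will have fewer events. Censoring at discontinuation may be informative, for example when subjects stop for lack of efficacy, so the display in step 3 must stay. That display is only as complete as the post-EOT recording that step 4 confirms.
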